Time 2: Pre- and Post-Clinic Visit: On the day of a clinic visit (for those patients who have been prescreened and found to be potentially eligible for an available clinical trial), clinic/research staff will meet with patients to remind them that the visit will be video recorded and to provide a copy of the patient intervention booklet, if needed. Just prior to and following the visit, patients will complete brief questionnaires (See Appendices H and I: Time 2 pre- and post questionnaires). If family members or companions are present, they will be told about the study and asked for consent (See Appendix C: Companion Information Sheet). Similarly, clinical staff who will be in the room during video recording will be provided an information sheet (See Appendix D: Health Care Provider Information Sheet.) Patients will receive a \$10.00 gift card following this visit. Also, patients will be asked whether they were offered a clinical trial; if they were not, they will be told that they are still in the study and may be contacted again in the future. They will continue to be tracked for up to a total of 4 visits or until the end of their participation. If they still receive no offer after a fourth visit, they will no longer be tracked. If they are offered a trial, they will proceed to Time 3.

Time 3: Follow-Up Interview: A week after the visit, research staff will contact patients (on the phone or in person as convenient to patients) who were offered a trial to conduct a brief interview (Appendix J: Time 3 Follow-Up Interview). This interview should take approximately 20 minutes. Patients will receive a third \$10.00 gift card at the end of this interview.

Time 4: Medical Record Review: Research staff will examine patient medical records to determine participating patients' disease status, co-morbidities, whether and when they were eligible for an available trial, whether they completed procedures for trial enrollment and/or enrolled in a trial, and trial characteristics (e.g., difficulty, complexity) that may affect physicians' decisions to offer a trial and/or patients' decisions to participate.

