The physician-focused intervention includes two components: a communication and an attitude/awareness component. The **communication component** consists of a **web-based** communication skills training module. The objective of the training module is to improve physicians' communication skills in general (e.g., patient-centeredness, shared decision making) and specific to discussing trials with patients. **Once physicians have signed the re-consent forms, they will be provided a link to a website that will allow them to participate in the training. The training includes a didactic video that provides information about the importance of recruiting a diverse population of patients to cancer clinical trials, and encourages them to reflect on communication skills that facilitate effective patient-centered communication and shared decision-making about trials. Training methods will include brief explanations and discussions and video illustrations. The web-based materials also include questions (via a Qualtrics survey) that assess physicians' attitudes and knowledge about clinical trials, prior to and following the training. The training module takes about 1.5 hours. Physicians receive Continuing Medical Education (CME) credit and \$100.00 gift card once they complete the training. The script to the didactic video and the Qualtrics survey are attached.**

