The training is based on communication theory that suggest that in clinical communication, participants exchange both informational and relational messages,³⁵ and the web-based training will include training in how to provide both. Skill-building in **informational communication** involves guidelines for discussing information patients need to make an informed decision about participating in a trial based on the International Ethical Guidelines for Biomedical Research Involving Human Subjects prepared by the Council for International Organizations of Medical Sciences (CIOMS) and the World Health Organization (WHO) (http://www.cioms.ch/frame_guidelines).⁵⁸ Skill-building in **relational communication** involves explanations and illustrations of communication strategies such as using organizing statements, eliciting questions and concerns (e.g., "Ask-Tell-Ask"), using lay language, assessing understanding by using the "teach-back" method, acknowledging and responding directly and empathically to questions and concerns, and using shared-decision making principles.⁵⁸⁻⁶³ To increase the likelihood the training has long-term effects on physician communication, physician participants will have the opportunity (optional) to follow up the training by individual consulting with [name].

The **attitude/awareness component** will take place after physicians complete the communication **component** and is designed to increase the likelihood that physicians will discuss and offer trials to their patients. **This component is also intended as a booster to the communication training module. This component consists of a reminder card to be provided to physicians each time one of their participating patients is found to be potentially eligible for a clinical trial, based on screening by the research staff. The reminder card includes the**

patient's name, the trials for which he is potentially eligible, a yes/no question eliciting the physician's decision about discussing and offering the patient the trial(s), and information about effective communication about clinical trials. The reminder card will be provided by secure email and/or in person within a few days of the patient's clinic visit. Research staff who give the reminder card in person to the physician will be very careful to ensure privacy and confidentiality because it contains sensitive information, including the patient's name. The reminder card is attached.

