Power and Sample Size Estimates. A within-subject design is used to evaluate the physician intervention and a randomized control trial is used to evaluate the patient intervention. However, the outcomes of both interventions will be modeled at the patient level in a single model. We used the person-level multi-site/block trial design within Optimal Design to conduct power analyses because the unit of analysis is the patient-physician visit and data from these visits will likely be more similar within physicians than between physicians. The first power analysis is based 216 patients not lost to attrition, who should be eligible for clinical trials and thus randomized into the patient-level intervention. (See Participants and Recruitment—p. 7) We define the *primary outcome* of our study as patients' decisions to enroll in clinical trials, where a "success" is defined as a patient deciding to enroll. Our primary objective (Aim 1) is to examine the extent to which patient- and physician-level interventions affect physician and patient trial-related decisions, and thus we seek a sample size that gives us sufficient power to detect both the main effect of intervention and important interaction effects. We chose GEE power analysis for nested binomial outcomes with within-cluster treatments⁶⁶ as the best available model to estimate power for our primary objective; such estimates are lacking for HLM models. With 24 physicians and 9 patients per physician (i.e., 216 patients), a Type I error rate (α) of .05, and ICC of .05, and probability of success under the null hypotheses (p_{H_0}) of .25, we are well powered to detect p_H of .35 ($b = 0.48$, odds-ratio = 1.61) with power > .99. Our secondary objective, (i.e., Aim 2) is to examine whether patient race influences the effectiveness of either patient- or physician-level interventions on our primary outcome, and we remain well

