Control variables: At the patient level of the model, we will control for factors such as decisional control preferences, relevant attitudes, health literacy, number of boosters received, disease severity, co-morbidities, whether there is an available clinical trial for the patient, and if so, characteristics of the trial (e.g., difficulty, complexity). At the physician level, we will control for relevant racial and professional attitudes, and decisional control preferences. Because the physician-focused phase involves a quasi-experimental design, we will also control factors that might threaten the internal validity of the intervention, such as time since study has begun, and number of previous interactions between patients and physicians.

Hypothesis 1a. Outcomes will be significantly improved in the patient intervention group, relative to the usual care group. To test hypothesis 1a, we will fit separate MLMs to examine continuous and binary outcomes assessed during or after each visit in which a trial was discussed. The focal independent variable will be the dummy-coded variable indicating whether the patient was in the usual care or intervention group. Support for hypothesis 1a will be indicated by a significant coefficient for this independent variable (i.e. intervention/usual care).

Hypothesis 1b. Outcomes will be significantly improved for patients after the physician intervention, as compared to outcomes before the physician intervention. The focal independent variable is the dummy-coded variable indicating whether or not the patient's physician has received the physician intervention at the time of the clinic visit. Note that this variable is a within-subject variable among the physicians; however, because we theorize that the patient-physician communication quality is central to offers and acceptance of clinical trials, this variable is introduced in the model at level-1 (patients). Support for hypothesis 1b will be indicated by a significant physician-intervention coefficient (i.e., pre/post physician intervention).

Hypothesis 1c. The combined effects of the two interventions will be multiplicative, rather than simply additive. The focal independent variable is the dummy coded variable for the product interaction term in the model. We expect the physician intervention to be more effective among patients who received the patient intervention; we expect a statistically significant positive coefficient for the interaction term.

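### The model testing Hypothesis 1b adjusts for an undefined 'number of boosters received'; the only booster described is the reminder card, which is part of the physician intervention under test

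*Combined protocol and SAP*

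**What the plan says.** All places are in the combined protocol and SAP.

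- **Control variables (Models for Aim 1).** The patient-level controls include "decisional control preferences, relevant attitudes, health literacy, number of boosters received, disease severity, co-morbidities". The list is introduced as examples. Boosters are not defined there or anywhere else. Time since study start and number of previous patient-physician interactions are also controlled.
- **Physician Intervention.** "The physician-focused intervention includes two components: a communication and an attitude/awareness component". Of the attitude/awareness component the plan says: "This component is also intended as a booster to the communication training module". That component is "a reminder card to be provided to physicians each time one of their participating patients is found to be potentially eligible for a clinical trial", and it "will take place after physicians complete the communication" component. The word booster is used nowhere else outside the control list.
- **Time 2: Pre- and Post-Clinic Visit.** Video recording and visit questionnaires are "for those patients who have been prescreened and found to be potentially eligible for an available clinical trial". For patients without an offer: "They will continue to be tracked for up to a total of 4 visits".
- **Power and Sample Size Estimates.** "the unit of analysis is the patient-physician visit".
- **Models for Aim 1 and Hypothesis 1b.** One multilevel model per outcome serves Hypotheses 1a, 1b and 1c. Hypothesis 1b is supported if the pre/post physician-intervention coefficient in that model is significant. No analysis of 1b without the booster covariate is planned, and nothing says that 1b means training net of cards.

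**The concern.** A covariate that exists only because the intervention was delivered is not a confounder of that intervention. If boosters are reminder cards, holding their number fixed removes from the Hypothesis 1b coefficient whatever benefit rises with the number of cards. The plan says the card is meant to make physicians more likely to discuss and offer trials, so it lies on the intended path to the outcomes.

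Hypothesis 1b is decided by this one coefficient. A physician intervention that works partly through repeated cards could therefore be reported as weak or absent. If the cards add nothing per card, the estimate is still less precise than it need be.

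**Working it through.** The plan gives no figure for this point. It gives an effect scale, which reproduces: ln[(.35/.65)/(.25/.75)] = ln 1.615 = 0.48.

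**1. Which counts can occur.** Cards start only after training, so the count is 0 at every pre-period visit. The trigger for a card (a patient found potentially eligible) is also the condition for a recorded visit, so as planned the count is at least 1 at every analysed post-period visit. With up to four visits per patient it runs from 1 to 4.

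**2. What the coefficient then means.** Write the model as a + b·post + c·prev + e·time + d·cards. A post-period visit with k cards differs from the pre-period by b + d·k, so b is the effect at k = 0, where there are no planned visits. If previous interactions count study visits only, cards = post × (prev + 1). The pre/post difference is then b + d·(prev + 1), and b is its value at prev = −1.

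**3. Size of the shift.** Assumed: 1/2/3/4 cards at 70/20/7/3% of post-period visits, true average effect 10 points. Mean cards = 0.7 + 0.4 + 0.21 + 0.12 = 1.43.

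| Source of benefit | Effect at k cards (points) | b without boosters | b with boosters |
|---|---|---|---|
| All linear per card | (10/1.43)·k = 6.99k | 10 | 0 |
| Half linear per card | 5 + 3.50k | 10 | 5 |
| Training, or any card | 10 | 10 | 10 |

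On the log-odds scale, an average of about 0.48 becomes 0, 0.24 and 0.48.

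**4. Loss of precision.** Assumed: half the visits in each period, time uniform on months 0–20 and 22–42, the same visit-number distribution in both periods, visit number independent of time within period, one card per post-period visit, physician random effects ignored. The variance inflation of b is 1 + δ′W⁻¹δ/4. Here δ is the post-minus-pre difference in covariate means and W is the average within-period covariance matrix.

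- Time: δ = 22, W = 20²/12 = 33.33, contribution 22²/33.33 = 14.52. Inflation 1 + 14.52/4 = 4.63. Adding previous interactions leaves this at 4.63, because their mean does not differ between periods.
- Cards: variance in the post-period = 2.61 − 1.43² = 0.5651, so W = 0.5651/2 = 0.2826.
- With previous interactions as study visits only, the part of W left after adjusting for them is 0.2826 − 0.2826²/0.5651 = 0.1413. Contribution 1.43²/0.1413 = 14.47. Inflation 1 + (14.52 + 14.47)/4 = 8.25.
- With previous interactions also counting earlier visits (assumed Poisson, mean 3; variance 3.5651), the part left is 0.2826 − 0.2826²/3.5651 = 0.2602. Contribution 7.86. Inflation 1 + (14.52 + 7.86)/4 = 6.595.

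| Post-period cards | Previous interactions | Inflation with boosters | Variance ratio to 4.63 | SE ratio |
|---|---|---|---|---|
| 70/20/7/3% | study visits only | 8.25 | 1.78 | 1.33 |
| 70/20/7/3% | plus earlier visits | 6.595 | 1.42 | 1.19 |
| 90/10% on 1/2 | study visits only | 18.07 | 3.90 | 1.98 |
| 90/10% on 1/2 | plus earlier visits | 11.45 | 2.47 | 1.57 |

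**5. Limiting case.** If every post-period visit has exactly one card, the count equals the pre/post dummy. The design matrix has rank 4 of 5, and b cannot be estimated.

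**6. Simulation on the binary scale.** Setup: 24 physicians × 9 patients, ICC .05, total log-odds ratio 0.48, logistic GEE in place of the multilevel model, no time or previous-interaction terms, 400 runs per scenario. Post-period cards were 70/15/10/5% or 40/30/20/10%.

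- Without the count, the mean estimate was 0.44–0.50.
- With the count, it was 0.23–0.27 if half the effect ran through cards, and −0.03 to −0.01 if all did.
- If none did, it was unbiased (0.47), but the SE rose about 1.7-fold and significant runs fell from 33.5–36% to 18.5–20%.

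This confirms the shift in the estimate. It does not confirm the SE ratios in step 4, because it omits the two planned controls.

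**7. Other hypotheses.** With the per-card benefit doubled in the patient-intervention arm and card counts unrelated to arm, the Hypothesis 1c coefficient was .050 with and without boosters. No distortion of a race interaction was computed.

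**The case against.** The strongest reply is that boosters may not be cards. The item is in the patient-level list, whereas cards go to physicians. Extra booklet copies at Time 2 or the optional follow-up consulting could be meant, and the physician intervention was to be developed later, so the list may predate the card. This keeps the finding conditional. But neither alternative is called a booster, and a count of booklet copies would be a post-randomisation covariate that moves the problem to Hypothesis 1a. A definition is needed either way.

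Other points, and what stands of each:

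- **The list is open.** True, but this item is named in it as a planned control.
- **Bias needs benefit that accumulates per card.** This stands. The card is specific to a visit, so an any-card effect is natural, and then only precision is lost. The plan also describes the card as reinforcing the training, so accumulation is not excluded.
- **The larger variance ratios need a narrow reading of previous interactions.** This stands. Patients may have been seeing the physician for up to a year, so 1.42 and 2.47 fit the wording better than 1.78 and 3.90.
- **The count could be cumulative per physician.** With six post-period cards per physician (an assumption) and calendar time in the model, inflation goes only from 4.63 to 4.78, a ratio of 1.03. Under linear benefit the coefficient is already .02 without boosters, because calendar time absorbs the rest. On that counting rule, removing boosters recovers little.
- **Centring would also work.** Centring the count within the post-period, with zero in the pre-period, restores .10 in all three scenarios of step 3 and inflation of 4.63. It is a valid alternative to removal.

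**Conclusion.** The concern holds. The term is undefined. On the only reading the documents support by name, the plan conditions the Hypothesis 1b coefficient on one of the two components of the intervention it is meant to evaluate. That is a specification error whatever its size.

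The size rests on assumptions about card counts, how they are counted, and how benefit relates to them. With counts per patient, a true 10-point effect appears as anything from 0 to 10 points. The variance ratio is 1.42 to 3.90 over the cases tried, and estimation fails if every post-period visit has one card. The harm is small if the count is cumulative per physician. Hypotheses 1a and 1c are little affected while card counts are similar in the randomised arms. The Aim 2 models inherit the covariate because they add race terms to the same model. Confidence is medium, because the meaning of boosters is inferred.

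**What to change.** 1. State in Control variables what boosters counts, who receives it, and whether it is counted per patient or per physician.
2. If it is the reminder card, delete it from every model that contains the physician-intervention term: the shared Aim 1 model for each outcome and the Aim 2 models. Keep calendar time and number of previous interactions. If the team prefers to keep the count, centre it within the post-period and set it to zero in the pre-period.
3. Restrict any card dose-response analysis to post-period patients and label it exploratory. The count rises with visit number, and patients reach later visits only if they have had no offer.

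The cost is one definition and one deleted covariate. No new data are needed and the sample size does not change.

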Overview. We propose to conduct two related interventions focused on patients and physicians and to evaluate the effects on the **primary outcome, patient decisions to enroll in a trial**, and the following secondary outcomes: (a) physician offers of a clinical trial, (b) quality of patient-physician communication during clinical interactions, (c) patient understanding of trials offered, and (d) patient enrollment in the trial. The first intervention is a patient-focused intervention targeting patients' attitudes and beliefs about their physician and their role in patient-physician interactions and their communication during clinic visits. The second intervention is a physician-focused intervention targeting physicians' attitudes and beliefs about their patients and discussing trials with them and their communication during clinic visits when trials may be discussed. (We stress that we will seek separate secondary IRB approval for this physician intervention, and this intervention will not be implemented without this separate approval and physician re-consent.) Aim 1 is to determine the independent and the combined effects of the interventions on outcomes. Aim 2 is to examine whether the magnitude of the effects of the intervention are different for African American versus White men. Aim 3 is to examine the extent to which the quality of patient-physician communication mediates the relationship between the intervention and outcomes. In the following sections, we provide details about research design and procedures.

Research Settings and Participants

Data Collection Sites. The proposed research will be conducted at two NCI-designated comprehensive cancer centers. Both sites provide prostate cancer care in catchment areas with large populations of African Americans and actively recruit patients to clinical trials through national and regional consortia. Both sites are active members of the Prostate Cancer Clinical Trials Consortium (PCCTC). In its four years of participation in the PCCTC, KCI/WSU has been involved in 32 therapeutic and biomarker prostate trials, 21 (66%) of which address advanced stage disease. From 2008-2013, JHKCC has participated in 46 therapeutic (and 4 other intervention) trials for advanced stage disease and 27 therapeutic (and 19 other intervention) trials for early stage disease.

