Time 0: Patient Recruitment: Participating physicians (or their designee with a clinical relationship) will examine their daily clinic schedule to identify eligible patients who will visit the clinic for a scheduled appointment. We received a waiver of HIPAA documentation to confirm participant inclusion eligibility, and written HIPAA documentation will be obtained at consent. Physicians (or designee) will inform these patients about the study and provide them with a study flyer during or immediately after the visit. (See Appendix E: Flyer). If patients are interested, clinic/research staff will meet with them as soon as possible to explain the study and obtain consent (See Appendix A: Patient Consent Form). At this point, patients will be assigned an ID number and will be asked to complete questionnaires on a tablet device (i.e., iPad) via Qualtrics. Qualtrics is widely used for data collection in both medical and nonmedical settings, and follows very high-level security procedures to protect participant data. The Qualtrics system encrypts data before transmission and is HIPAA compliant. Patients will be asked to complete questionnaires (See Appendix F: Patient Time 0 Questionnaires) including: demographic information, date of prostate cancer diagnosis, preferences for future contact (during study participation), health status, perceived economic burden, health literacy, trust in the medical profession, group-based medical mistrust, and receptivity to discussing a clinical trial. We anticipate these questionnaires will take approximately 20 minutes. Patients will receive a \$20 gift card at this time. Then, clinic/research staff will track patients' scheduled visits until they become potentially eligible for an available clinical trial.

Time 1: 1-2 Weeks Prior to First Clinic Visit After Enrollment: Prior to a patient's scheduled appointment with a participating physician, clinic/research staff will determine whether the patient is potentially eligible for an available clinical trial. If there is no trial available, the patient will not be contacted, and tracking will continue until

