the next scheduled visit. If/when the patient is found to be potentially eligible for an available trial, clinic/research staff will contact him according to the communication/contact preferences he provided at Time 0. They will remind him about the study and ask him if he is willing to meet with research staff at a convenient place and time to complete the Time 1 (baseline) questionnaire (Appendix G: Time 1 Questionnaires), again administered to the participant through Qualtrics on a tablet device (e.g., iPad) or over the phone. The research staff will NOT directly inform patients about their eligibility. If asked, they will tell patients this is up to the physician and clinical staff. Once the questionnaire is completed, an automated computer program provided by Qualtrics will randomly assign the patient to either the usual care or intervention group. Intervention group patients will receive the intervention at this time, or prior to their upcoming appointment, in the form of a booklet (See Appendix M: Patient Intervention Booklet; see below for details). All patients will receive a \$20.00 gift card and be told that their next clinic visit may be video recorded. This visit should take < one hour.

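### The yes/no trial-availability control is nearly constant among analysed patients and no listed covariate counts open trials, so an abrupt change in the trial menu near the physician intervention could bias Hypothesis 1b

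*Combined protocol and SAP*

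**What the plan says.** The Control variables paragraph under Models for Aim 1 lists patient-level covariates, including "whether there is an available clinical trial for the patient, and if so, characteristics of the trial (e.g., difficulty, complexity". Because the physician phase is quasi-experimental, it adds controls meant to protect the before/after contrast, "such as time since study has begun, and number of previous interactions between patients and physicians". The form of the time term is not given. Both lists are introduced as examples, so neither is exhaustive. The Conceptual Model section names trial availability as affecting offers and decisions and promises to include it in the analyses.

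The route into the analysis is set out under Patient Procedures. At Time 1, "If there is no trial available, the patient will not be contacted"; contact, the baseline questionnaire and randomisation follow "If/when the patient is found to be potentially eligible for an available trial". Time 2 recording is likewise confined to men who passed that screen. The power section describes the 216 analysed patients as men "who should be eligible for clinical trials and thus randomized into the patient-level intervention", and Participants and Recruitment describes the same 216 as recorded while discussing a trial.

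Hypothesis 1b contrasts visits before and after the same physicians receive the intervention, with 20 months on each side and no physicians left untrained. A per-patient list of trials is described only for the reminder card used after the intervention, which shows "the trials for which he is potentially eligible".

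**The concern.** In a before/after comparison, the set of open trials is an obvious background exposure. If the typical man can be offered two trials after the intervention and one before it, offers and decisions to enrol may rise with no change in what physicians do. If the menu shrinks, a real effect may be hidden.

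The plan recognises this and includes an availability covariate. But availability is also the gate to randomisation. A covariate with the same value for almost every analysed patient cannot separate the menu from the phase. The coefficient at stake is the pre/post physician-intervention term in Hypothesis 1b.

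**Working it through.** **1. The planned effect.** Power and Sample Size Estimates gives success rates of .25 and .35. Odds are .25/.75 = .3333 and .35/.65 = .5385. The ratio is 1.615 and its log 0.480, which match the plan's 1.61 and 0.48. This is the yardstick below; the stated power plays no part in this point.

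**2. Does the availability term vary?** No contact without an available trial; randomisation only after the screen; recording only for men who passed it. The indicator is yes for essentially everyone analysed. It could vary if coded from the Time 4 chart review of whether and when the man was eligible, but that review is listed after the visit and follow-up interview.

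**3. What do the other controls cover?**

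| Change in the menu | Listed control that could absorb it |
|---|---|
| Gradual drift over the study | Elapsed study time |
| Shift in a recorded feature (difficulty, complexity) | Trial characteristics |
| Abrupt change near months 20–22 in the number of trials per man | None listed |

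**4. Simulation of time and characteristics.** Assumptions: 216 patients, 108 in months 0–20 and 108 in months 22–42; true physician effect zero; 30% of men initially face a more favourable menu; that menu has log odds ratio 1.5 on the decision, with intercept −1.6. There were 2,000 runs per row, with no physician clustering. Cells show the mean false log odds ratio for the physician phase and, in brackets, the rejection rate at a nominal 5%.

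| Change in favourable share | No control | Linear time | Feature itself recorded |
|---|---|---|---|
| Step, +20 points | 0.29 (16%) | 0.31 (8%) | −0.01 (5%) |
| Step, +40 points | 0.58 (48%) | 0.59 (15%) | −0.01 (4%) |
| Drift, +20 points | 0.16 (8%) | −0.02 (4%) | 0.00 (4%) |
| Drift, +40 points | 0.32 (19%) | 0.01 (4%) | 0.01 (5%) |

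Hand check of the step rows: success is 1/(1+e^1.6) = .168 without and 1/(1+e^0.1) = .475 with the favourable menu. Mixed rates at shares of 30%, 50% and 70% are .260, .322 and .383. Log odds differences from the first are 0.30 and 0.57, in line with the simulation.

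Linear time removes drift but leaves the step bias intact. Its lower rejection rates in the step rows reflect a larger standard error, not less bias. The last column applies only if the feature that changed is the one recorded; the number of trials is not among the characteristics the plan names.

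**5. Cost of the time term.** With visits uniform within each period, the phase means are months 10 and 32. Between-phase variance is 11² = 121 and within-phase variance 20²/12 = 33.3, so r² = 121/154.3 = .784. Variance inflation is 1/(1 − .784) = 4.6 and the standard error ratio √4.6 ≈ 2.15. The simulation agrees: about 0.30 rises to about 0.65.

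**6. Illustration for the number of trials (all inputs assumed except .25).** Let success be .25 with one trial and, treating two trials as independent chances, 1 − .75² = .4375 with two. The rate is then share × .4375 + (1 − share) × .25.

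| Share of men with two trials | Success rate | Change from 20% |
|---|---|---|
| 20% | .2875 | – |
| 30% | .306 | +1.9 points |
| 40% | .325 | +3.8 points |
| 50% | .344 | +5.6 points |

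A shrinking menu gives the same sizes with the opposite sign. If a second trial adds nothing to a man's chance of saying yes, the change is zero.

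**The case against.** The strongest reply is that the plan does not rely on the availability indicator alone. The same sentence goes on to trial characteristics, and the paragraph adds elapsed time precisely because the physician phase is not randomised. By the simulation above, these remove a gradual drift, and even an abrupt shift in a recorded feature. This stands. A reader might infer that availability is the only safeguard and that any change in trial supply will therefore be taken for an intervention effect; the documents do not support that.

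Nor do they show that the menu will change abruptly. Data Collection Sites says that "KCI/WSU has been involved in 32 therapeutic and biomarker prostate trials" over four years, but that is a cumulative count and does not measure openings, closures or trials per eligible man.

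The illustration is also generous. One man's decisions about two trials share his attitudes and his physician, and active participation ends at a trial offer, so two independent chances overstates the shift. The largest figure, 5.6 points, is below one standard error of a 108-versus-108 difference: √[(.2875 × .7125 + .344 × .656)/108] ≈ 6.3 points. Both objections stand. The second limits how visible the bias would be, but does not make the covariate informative.

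It might also be inferred that Hypotheses 1c and 2 are biased as a matter of course. Patients are randomised within each phase, so a menu change that moves both arms equally on the log-odds scale cancels from the product term. Bias there needs a menu effect that differs by arm or by race, and nothing in the documents indicates one.

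What survives is narrow: an abrupt change in the number of trials per man has no listed control. The characteristics covariate does not clearly fill the gap, because the plan does not say which trial is coded when a man qualifies for several. If it is the trial offered, the covariate depends partly on a physician choice that the intervention aims to influence.

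**Conclusion.** The point holds in limited form. The yes/no availability control adjusts for almost nothing among analysed patients, because availability is the condition for being analysed. Gradual drift and changes in recorded features can be handled by the other controls. An abrupt change near the physician intervention in the number of trials each man could be offered would not be, and with no concurrent untrained physicians Hypothesis 1b could be biased in either direction. The randomised comparison in Hypothesis 1a is not affected.

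The documents give no data on the number of trials per man, so the size cannot be estimated. The figures of 1.9 to 5.6 points rest on assumed shares and on independent chances, and are best read as upper values for those shares. The simulated log odds ratios of about 0.3 and 0.6 under a step, against the planned 0.48, rest on an assumed menu effect of 1.5 and ignore clustering. The case for acting is that the planned covariate is nearly empty and a useful replacement is cheap, not that bias has been shown.

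**What to change.** In the Control variables paragraph, replace the yes/no availability term with the number of open trials for which staff find the patient potentially eligible at Time 1, plus an indicator of whether any is for advanced disease. Record both before randomisation on one screening form used identically in both phases. Before the physician intervention the list should not go to physicians, since the reminder card is part of that intervention. Identical recording matters: if trials are listed more fully once reminder cards are in use, the count would rise for that reason alone.

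If screening before the intervention is already complete, derive the count the same way in both phases from screening records and trial opening and closing dates.

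Keep the time and trial-characteristics controls, and state the form of the time term in the same edit. An analysis of Hypothesis 1b limited to men eligible for a trial open in both phases is optional and supportive only: it shrinks a sample of 216 and does not hold the rest of each man's menu fixed.

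The cost is a few minutes more screening record per patient, one or two covariates and a short change to the analysis text. Staff already screen each patient against available trials.
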